11.4. Safety Analyses

All safety analyses will be performed on the FAS.

No formal statistical testing of safety data is planned. Safety data will be tabulated by vaccine regimens and pooled placebos and will be analyzed descriptively. The severity of abnormal symptoms, vital signs, AEs and abnormal laboratory values will be graded based on the toxicity table from the FDA “Toxicity Grading Scale for Healthy Adult and Adolescent Volunteers Enrolled in Preventive Vaccine Clinical Trials (September 2007, see [Attachment 2](#))”.

Adverse Events

The verbatim terms used in the eCRF by investigators to identify AEs will be coded using the Medical Dictionary for Regulatory Activities (MedDRA). All reported AEs (solicited local, solicited systemic, and unsolicited), event-related diary information, and all SAEs with onset or worsening within 28 days after each vaccination will be included in the analysis. For each AE, the percentage of participants who experience at least one occurrence of the given event will be summarized by vaccine schedule.

Summaries, listings, datasets, or narratives may be provided, as appropriate, for those participants who die, who discontinue study vaccine due to an AE, or who experience a severe AE or an SAE.

Summaries and listings may be provided separately for AEs with onset outside the above defined timeframe that were reported pre-dose at the moment of subsequent vaccinations for studies using multiple doses.

Solicited local (at injection site) and systemic AEs will be summarized descriptively. The overall frequencies per vaccine group as well as frequencies according to severity and duration will be calculated for solicited AEs. In addition, the number and percentages of participants with at least 1 solicited local (at injection site) or systemic AE will be presented. Frequencies of unsolicited AEs, separately for all and vaccination-related only, will be presented by System Organ Class and preferred term, while those of solicited AEs will be presented only by preferred term.

Clinical Laboratory Tests

Laboratory data will be reported by type of laboratory test. Actual values and changes from baseline will be summarized for each laboratory analyte at baseline and at each scheduled time point (ie, Visits 1, 4 and 8). Graphical presentation of changes in laboratory tests will be made as applicable. Baseline refers to the last value prior to first vaccination.

Laboratory abnormalities will be determined according to the FDA toxicity grading tables (see [Attachment 2](#)) or, for tests for which no grades are available, in accordance with the normal ranges of the clinical laboratory. Any laboratory value shown as a “graded” value in the FDA table that is within the institutional normal ranges will not be graded for severity.

Vital Signs

Values and changes from baseline of supine heart rate and blood pressure (systolic and diastolic) will be summarized at each scheduled time point (baseline refers to the last value prior to first vaccination). The percentage of participants with values beyond pre-specified limits will be reported.

Physical Examination

Physical examination findings at baseline will be summarized. Abnormalities during the study will be listed.

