2. OBJECTIVES, ENDPOINTS, AND HYPOTHESIS

2.1. Objectives and Endpoints

Primary

Objectives	Endpoints
Primary To assess safety and reactogenicity of the 3 vaccine regimens.	
 • Solicited local and systemic adverse events (AEs) for 7 days after each vaccination. • Unsolicited AEs from the time of informed consent form (ICF) signature until 28 days after the first vaccination, and thereafter, until 28 days after the second vaccination. • Serious adverse events (SAEs) throughout the study.

Secondary

Objectives	Endpoints
To assess immunogenicity of the 3 vaccine regimens.	T cell responses to the separate or combined protein peptide pools of HPV16 and HPV18 E2, E6 and E7 proteins, including specific CD4 ⁺ and CD8 ⁺ T cells producing IFN γ , tumor necrosis factor alpha (TNF α), or interleukin 2 (IL-2) (combined cytokine expression may also be assessed) will be determined by flow cytometry.

Exploratory

Objectives	Endpoints

To assess the frequency and kinetics of clearance of
 
 • persistent or recently diagnosed HPV16 and HPV18 infection (combined^a) and • persistent or recently diagnosed HPV16 infection and • persistent or recently diagnosed HPV18 infection 
of the 3 vaccine regimens compared to placebo over the study period.
	
Healthcare provider- and self-collected cervical samples obtained over the study period will be genotyped by a qualitative HPV genotyping test (Cobas[®], Roche) and a quantitative HPV PRC genotyping test to evaluate HPV16 and/or HPV18 viral clearance^b, defined as:
 
 • A negative HPV16 genotype over the study period after having a baseline HPV16 infection (persistent or recently diagnosed); OR • A negative HPV18 genotype over the study period after having a baseline HPV18 infection (persistent or recently diagnosed).
To assess regression of CIN1 and concomitant clearance of HPV16 and/or HPV18 infection of the 3 vaccine regimens compared to placebo over the study period.	
 • Regression of CIN1: A colposcopic impression of normal after having a baseline of CIN1, AND concomitant clearance of baseline (persistent or recently diagnosed) HPV16 and/or HPV18 infection (as defined above).

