9.1.4. Vaccination and Follow-up Period (Day 1 to Day 366)

9.1.4.1. Vaccination (Day 1, and Day 57)

- **Day 1/Day of Randomization/Vaccination 1: Visit 2**

After an abbreviated physical examination (at the discretion of the investigator), measurement of vital signs, urine pregnancy test (for women of childbearing potential), self-collected cervico-vaginal sample for type-specific HPV16 and HPV18 PCR, HSV-2 serology test, and pre-vaccination symptoms check, eligible participants will be randomized as described in Section 5. If a participant's clinical status changes (including any available laboratory results or receipt of additional medical records) after screening but before the first dose of study vaccination is given such that she no longer meets all eligibility criteria, then the screening laboratory tests should be repeated and the Day 1 visit rescheduled, or the participant should be excluded from participation in the study. Pre-dose samples for baseline immunogenicity assessments will be collected. Before vaccination, the investigator must check for any symptoms of an acute illness or oral temperature ≥ 38.0 °C. If the vaccination visit cannot be rescheduled within the allowed window or the contraindications to vaccination persist, the sponsor should be contacted for further guidance.

Administration of first dose of study vaccine.

After vaccination, participants will remain under observation at the study site for at least 30 minutes for presence of any acute reactions and solicited events and will be allowed to leave the vaccination site at approximately 45 minutes post-vaccination. Any unsolicited, solicited local or systemic AEs and vital signs will be documented in the eCRF by study-site personnel following this observation period.

Participants will be provided with a participant diary, thermometer, and ruler to measure and record oral body temperature, solicited local and systemic AEs for 7 days post-vaccination.

Unsolicited AEs will be recorded on the AE page of the eCRF from the time of ICF signature until 28 days after the first vaccination, together with information about any concomitant medications. SAEs will be collected until the study end (Day 366).

- **Day 57/Vaccination 2: Visit 6**

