12. ADVERSE EVENT REPORTING

Timely, accurate, and complete reporting and analysis of safety information from clinical studies are crucial for the protection of participants, investigators, and the sponsor, and are mandated by regulatory agencies worldwide. The sponsor has established Standard Operating Procedures in conformity with regulatory requirements worldwide to ensure appropriate reporting of safety information; all clinical studies conducted by the sponsor or its affiliates will be conducted in accordance with those procedures.

Method of Detecting AEs and SAEs

Care will be taken not to introduce bias when detecting AEs or SAEs. Open-ended and nonleading verbal questioning of the participant is the preferred method to inquire about AE occurrence.

Solicited Adverse Events

Solicited AEs are predefined local (at the injection site) and systemic events for which the participant is specifically questioned and symptoms of which are noted by participants in their diary (see Section 9.1.1).

Unsolicited Adverse Events

Unsolicited AEs are all AEs for which the participant is NOT specifically questioned in the participant diary.

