12.3.2. Serious Adverse Events

All SAEs occurring from the time of ICF signature until the end of the study must be reported to the appropriate sponsor contact person by study-site personnel within 24 hours of their knowledge of the event.

Information regarding SAEs will be transmitted to the sponsor using the SAE Form, which must be completed and signed by a physician from the study site, and transmitted to the sponsor within 24 hours. The initial and follow-up reports of an SAE should be made by facsimile (fax) and/or through secure email.

All SAEs that have not resolved by the end of the study, or that have not resolved upon discontinuation of the participant's participation in the study, must be followed until any of the following occurs:

- The event resolves
- The event stabilizes
- The event returns to baseline, if a baseline value/status is available
- The event can be attributed to agents other than the study vaccine or to factors unrelated to study conduct
- It becomes unlikely that any additional information can be obtained (participant or health care practitioner refusal to provide additional information, lost to follow-up after demonstration of due diligence with follow-up efforts)

Suspected transmission of an infectious agent by a medicinal product will be reported as an SAE. Any event requiring hospitalization (or prolongation of hospitalization) that occurs during the course of a participant's participation in a study must be reported as an SAE, except hospitalizations for the following:

- Hospitalizations not intended to treat an acute illness or AE (eg, social reasons such as pending placement in long-term care facility)
- Surgery or procedure planned before entry into the study (must be documented in the eCRF). Note: Hospitalizations that were planned before the signing of the ICF, and where the underlying condition for which the hospitalization was planned has not worsened, will not be considered SAEs. Any AE that results in a prolongation of the originally planned hospitalization is to be reported as a new SAE.

The cause of death of a participant in a study during the entire study period, whether or not the event is expected or associated with the study vaccine, is considered an SAE and must be reported.

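### Section 11.4 limits the SAEs named for the adverse event analysis to 28 days after each dose, but the primary endpoint is SAEs throughout the study

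*Protocol*

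**What the plan says.** Section 2.1 (and the Synopsis) lists three primary safety endpoints, each with its own period. Solicited AEs run for 7 days after each vaccination. Unsolicited AEs run from consent "until 28 days after the first vaccination, and thereafter, until 28 days after the second vaccination". The third endpoint is "Serious adverse events (SAEs) throughout the study", with no post-dose window.

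Collection matches the endpoint. Section 12.3.2 states: "All SAEs occurring from the time of ICF signature until the end of the study must be reported". Section 9.1.4.1 gives Day 366 as the end of SAE collection, and Section 9.2.1 says that outside the 28-day periods reporting is limited to SAEs.

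On analysis, Section 11.4 opens with a general commitment: "Safety data will be tabulated by vaccine regimens and pooled placebos and will be analyzed descriptively". Its Adverse Events paragraph then says what goes in: reported solicited and unsolicited AEs, diary information, and "all SAEs with onset or worsening within 28 days after each vaccination will be included in the analysis". Other SAE output is optional: "Summaries, listings, datasets, or narratives may be provided, as appropriate, for those participants who die", and likewise for participants who have an SAE. A further optional output covers AEs outside the stated timeframe, but only those reported pre-dose at a later vaccination.

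Section 11.7 says that the primary analysis includes safety data to the Week 26 visit and that the final analysis takes in additional safety data collected afterwards.

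**The concern.** This is a first-in-human trial with safety as its primary objective, and SAEs are the only primary endpoint defined over the whole study. The sentence that names the SAEs for the analysis uses the period that belongs to the unsolicited AE endpoint. Someone programming from Section 11.4 could produce an SAE table limited to the two 28-day windows. Someone working from Sections 2.1 and 11.7 would tabulate every SAE to the data cut. The protocol does not say which governs.

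The mismatch is widest for participants who receive only Dose 1. Section 10.2 stops vaccination after, among other reasons, a related SAE, and keeps those participants in follow-up to Week 52. They have a single 28-day window, and the optional listing tied to a later vaccination cannot apply to them.

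The problem lies in the analysis wording. SAE collection, expedited reporting and monitoring are unaffected.

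**Working it through.** The protocol gives no figure of its own on this point, so the check is a comparison of texts and a day count.

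**Possible readings of the Section 11.4 sentence**

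1. *The 28-day phrase governs the whole list.* SAEs with onset outside the windows are not covered, contrary to Section 2.1.
2. *The phrase governs the SAE item and sets its scope.* The result for SAEs is the same.
3. *The phrase governs the SAE item, but late SAEs enter earlier in the sentence as reported unsolicited AEs.* Section 12 gives some support: "Unsolicited AEs are all AEs for which the participant is NOT specifically questioned in the participant diary". The separate SAE item then has no purpose, and late SAEs enter under a category whose endpoint ends 28 days after each dose.

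Readings 1 and 2 conflict with the endpoint. Reading 3 avoids the conflict only by leaving the SAE clause without function.

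**Contrast within the protocol.** The pausing rules in Section 11.9 cover AEs up to 28 days after each vaccination and SAEs throughout the study. An SAE on Day 120 would count for pausing but fall outside the Section 11.4 sentence.

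**Inputs for the day count:** Dose 1 on Day 1, Dose 2 on Day 57 (±7), Week 26 visit on Day 183, last visit on Day 366 (±14), screening of up to 42 days (Synopsis, Time and Events Schedule).

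*Both doses, to Day 366*
- Follow-up: 366 − 1 = 365 days.
- Inside: Day 1 to 29 (28) + Day 57 to 85 (28) = 56; 56/365 = 15.3%.
- Outside: Day 29 to 57 (28) + Day 85 to 366 (281) = 309; 309/365 = 84.7%.
- After Day 85, none of the 281 days is inside.

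*Both doses, to Week 26*
- Follow-up: 183 − 1 = 182 days.
- Inside: 56/182 = 30.8%. Outside: 28 + 98 = 126; 126/182 = 69.2%.

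*Dose 1 only*
- To Day 366: 28/365 = 7.7% inside; 337/365 = 92.3% outside.
- To Week 26: 28/182 = 15.4% inside; 154/182 = 84.6% outside.

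*Visit windows, both doses.* The outside share depends only on the last visit, because moving Dose 2 shifts days between the two gaps. Last visit on Day 352: 295/351 = 84.0%. Last visit on Day 380: 323/379 = 85.2%.

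SAEs between consent and first vaccination, a period of up to 42 days, also fall outside the windows.

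**Example.** A related SAE begins on Day 40 and vaccination is stopped. It lies after the Dose 1 window, there is no Dose 2 window, and no later vaccination triggers the optional pre-dose listing. Section 11.4 read literally does not name it; Sections 2.1 and 11.7 do include it.

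**The case against.** The sentence says what will be included; it does not say that anything is left out. A late SAE is still a reported AE, and the Section 12 definition of unsolicited AEs has no time limit, so it can enter through the first part of the same sentence. Section 11.7 commits in firm terms to safety data to Week 26 and beyond. Since late adverse event reporting is limited to SAEs, that commitment would have little adverse event content unless late SAEs were analysed. The Synopsis safety text carries no 28-day limit. The analysis is descriptive, in about 66 women, and Section 11 leaves specifics to the SAP. The percentages describe calendar time under the restrictive readings, not events lost.

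Much of this stands. Omission of late SAEs is not certain, the percentages do not measure lost events, and the protocol gives neither a late SAE rate nor an expected number of Dose-1-only participants.

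It does not remove the mismatch. The compatible reading makes the SAE clause redundant and relies on a category whose own endpoint closes at 28 days. The Section 11.7 commitments are the text with which the specific sentence conflicts. Optional output does not secure a primary endpoint. This is also more than detail deferred to the SAP, because the protocol states an inclusion rule and the SAP author would have to choose which passage to follow.

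**Conclusion.** The concern holds. The inclusion sentence in Section 11.4, followed literally, gives an SAE analysis that does not match the primary endpoint in Section 2.1 or the planned analyses in Section 11.7. On the nominal schedule 84.7% of follow-up after first vaccination lies outside the named windows (84.0% to 85.2% across the visit windows), and 92.3% for a participant who stops after Dose 1 and is followed to Week 52. These figures assume that the 28-day phrase limits SAEs, and they count days, not expected SAEs. The conclusion that the wording is mismatched does not depend on them. It should be fixed before analysis; confidence is high that the text conflicts, with no claim that late SAEs would in fact be dropped.

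**What to change.** Reword the inclusion sentence in Section 11.4 so that each AE class carries the period of its own endpoint:

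- solicited AEs: 7 days after each vaccination;
- non-serious unsolicited AEs: the 28-day window after each vaccination;
- SAEs: all events over the whole study, tabulated by regimen and pooled placebo, to Week 26 at the primary analysis and to Week 52 at the final analysis, with SAEs before first vaccination shown separately.

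The split already used in the Section 11.9 pausing rules can serve as the model. Table layout can stay in the SAP. The cost is one reworded sentence; no new data are needed and nothing in the conduct of the trial changes.

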11.5. Immunogenicity Analyses

The immunogenicity analyses will be performed on the PPI set. An additional analysis will be done for the FAS.

Immunogenicity analyses for HPV16 and HPV18 participants will be performed either combined or by HPV type (HPV16 or HPV18), and by infection type (persistent or recently diagnosed).

No formal hypothesis on immunogenicity will be tested. Descriptive statistics (geometric mean and 95% CI, or median and quartile range [Q1-Q3], as appropriate) will be calculated for

continuous immunological parameters at all time points. Graphical representations of immunological parameters will be made as applicable. Frequency tabulations will be calculated for discrete (qualitative) immunological parameters as applicable.

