
 To explore potential immune correlates for viral clearance. 	
 Immunogenicity endpoints of HPV-specific cellular or humoral responses described above, determined at multiple time points after vaccination will be used to explore potential immune correlates of viral clearance of HPV16 and/or HPV18.

^a The sum of women who clear an HPV16 infection plus women who clear an HPV18 infection

^b Women who receive CIN treatment will be considered as not clearing an HPV infection.

Refer to Section 9 for evaluations related to endpoints.

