A diagram of the study design is provided in [Figure 2](#) and [Figure 3](#).

[figure not shown]
Table 4: Study Design

HPV Type*	Regimen	Vaccine Regimen		Phase 1					Phase 2a	Total
		Day 1	Day 57 (Week 8)	Step 1 sentinel; low dose	Step 2 completion Phase 1; low dose	Step 3 Sentinel dose escalation high & mixed regimens	Step 4 completion Phase 1; high & mixed regimens	Subtotal		
16	Regimen 1a (Ad26 low dose)	Ad26.HPV16 (5x10 ¹⁰ vp)	MVA.HPV16/18 (2x10 ⁸ Inf.U)	1	3	-	-	4	-	4
16	Regimen 2a (Ad26 high dose)	Ad26.HPV16 (1x10 ¹¹ vp)	MVA.HPV16/18 (2x10 ⁸ Inf.U)	-	-	1	3	4	6	10
16	Regimen 3 (mixing of Ad26)	Ad26.HPV16 (5x10 ¹⁰ vp) + Ad26.HPV18 (5x10 ¹⁰ vp)	MVA.HPV16/18 (2x10 ⁸ Inf.U)	-	-	1	3	4	6	10
16	Control	Placebo (1.0 mL)	Placebo (0.5 mL)	1	1	1	2	5	4	9
Total HPV16				2	4	3	8	17	16	33
18	Regimen 1b (Ad26 low dose)	Ad26.HPV18 (5x10 ¹⁰ vp)	MVA.HPV16/18 (2x10 ⁸ Inf.U)	1	3	-	-	4	-	4
18	Regimen 2b (Ad26 high dose)	Ad26.HPV18 (1x10 ¹¹ vp)	MVA.HPV16/18 (2x10 ⁸ Inf.U)	-	-	1	3	4	6	10
18	Regimen 3 (mixing of Ad26)	Ad26.HPV16 (5x10 ¹⁰ vp) + Ad26.HPV18 (5x10 ¹⁰ vp)	MVA.HPV16/18 (2x10 ⁸ Inf.U)	-	-	1	3	4	6	10
18	Control	Placebo (1.0 mL)	Placebo (0.5 mL)	1	1	1	2	5	4	9
Total HPV18				2	4	3	8	17	16	33*
Total				4	8	6	16	34	32	66

[figure not shown]
PI/SPR IDMC PI/SPR IDMC

Ad26=adenovirus serotype 26; HPV=human papillomavirus; Inf.U=infectious unit; MVA=modified vaccinia Ankara; vp=viral particles

* If enrollment is slow for HPV18-infected participants, up to 8 HPV18-infected participants can be replaced by HPV16-infected participants, hence a minimum of 25 HPV18 participants will be allowed. The decision will be taken during Step 5.

Figure 2: Schematic Overview of the Study - HPV16 Infected Participants

* Two sentinel participants from the HPV18 group are required for IDMC review in step 2 before starting step 3.

Figure 3: Schematic Overview of the Study - HPV18 Infected Participants

* Two sentinel participants from the HPV16 group are required for IDMC review in step 2 before starting step 3.

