Regimen 1: Separate administration of low dose Ad26.HPV16 or Ad26.HPV18 (matching the participant's underlying HPV infection) at Day 1, followed by MVA.HPV16/18 at Day 57 will be part of the ascending dose design. We will assess safety initially among a small group of participants immunized with this low dose Ad26.HPV16 or 18 regimen. After satisfactory completion of the safety review the next participants enrolled may receive the higher dose regimens (2 and 3).

Regimen 2: Separate administration of 1×10^{11} vp of Ad26.HPV16 or 1×10^{11} vp of Ad26.HPV18 (matching the participant's underlying HPV infection) at Day 1, followed by MVA.HPV16/18 at Day 57 will be used to assess safety and immunogenicity.

Regimen 3: Mixing of a single-syringe administration of 5×10^{10} vp of Ad26.HPV16 and 5×10^{10} vp of Ad26.HPV18 (ie, Ad26.HPV16/Ad26.HPV18) at Day 1, followed by MVA.HPV16/18 at Day 57 will be used to assess safety and immunogenicity and data will be compared to regimen 2.

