5. STUDY VACCINE ALLOCATION AND BLINDING

Study Vaccine Allocation

Randomization will be stratified by HPV type (16 and 18) and within each HPV type, randomization will be performed in different steps (see Table 1). Between the steps, randomization will be halted until a 24-hour and 7-day review by the PI and SRP or an IDMC review have been performed. For HPV16 infected participants the following randomization steps will take place:

- Step 1: 2 participants will be randomly assigned to receive low dose Ad26.HPV16 or placebo. These participants may be randomized on the same day.
- Step 2: 4 participants will be randomly assigned to receive low dose Ad26.HPV16 (3 participants) or placebo (1 participant). There will be a staggered interval of 7 days between the vaccination of each of these 4 participants.
- Step 3: 3 participants will be randomly assigned to receive high dose Ad26.HPV16 or the Ad26.HPV16/Ad26.HPV18 mix or placebo. These participants may be randomized on the same day.
- Step 4: 8 participants will be randomly assigned to receive high dose Ad26.HPV16 (3 participants) or the Ad26.HPV16/Ad26.HPV18 mix (3 participants) or placebo (2 participants). There will be a staggered interval of 7 days between the vaccination of each of these 8 participants.
- Step 5: 16 participants will be randomly assigned to receive high dose Ad26.HPV16 (6 participants), Ad26.HPV16/Ad26.HPV18 mix (6 participants) or placebo (4 participants). No more than 5 participants will be vaccinated per week.

The same randomization process will be used for the HPV18-infected participants.

If enrollment is slow for HPV18-infected participants, up to 8 HPV18-infected participants can be replaced by HPV16-infected participants, hence a minimum of 25 HPV18 participants will be allowed; the decision will be taken during Step 5.

Blinding

The participants, study-site personnel (including vaccine administrator) and investigator will be blinded to study vaccine allocation throughout the study, except for the pharmacist or qualified staff member with primary responsibility for study vaccine preparation and dispensing.

At the time of the primary analysis, the study will be unblinded for sponsor personnel (including medical personnel, biomarker lead, virologist, statistician, programming and data management). Participants, clinical staff and study-site personnel will remain blinded to the study vaccine allocation until the end of the study.

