9.2.2. Immunogenicity

Venous blood samples will be collected for the determination of humoral and cellular responses, according to the [Time and Events Schedule](#). Sample collection and processing will be performed by the staff at the clinical site according to current versions of the approved clinical site's standard procedures.

Since the vaccine targets a cellular therapeutic response, the emphasis will be on the assessment of cellular immune responses. During the study, cellular immune responses will be measured in all participants at 5 time points during the 12-month follow-up period after the first vaccination:

- pre-Dose 1, pre-Dose 2, at 21 days, 6 months post-Dose 2 and 12 months post-Dose 1

Cellular immunological assays are summarized in [Table 5](#). Humoral immunological assays are summarized in [Table 6](#). Exploratory analyses may be performed, including, but not limited to, the listed assays. Baseline and post-vaccination samples will be used for the characterization of immunological assays.

Table 5: Summary of Immunogenicity Assays (Cellular)

Assay	Purpose
Secondary endpoints	
ICS	Analysis of T cell responses to the separate or combined protein peptide pools of HPV16 and HPV18 E2, E6 and E7 proteins, including specific CD4 ⁺ and CD8 ⁺ T cells producing IFN γ , TNF α , or IL-2 (combined cytokine expression may also be assessed)
Exploratory endpoints	
ICS	Analysis of other cellular responses to the separate or combined protein peptide pools of HPV16 and HPV18 E2, E6 and E7 proteins (including, but not limited to, mucosa-homing markers, Th17, Th2, Treg, cytolytic markers, activation markers, exhaustion markers)
Transcriptome analysis	Analysis of gene expression patterns to provide phenotypic and functional characterization of PBMCs ex vivo or after stimulation with HPV16 and/or HPV18 E2, E6, and/or E7 peptide pools.
ELISpot responses	Enumeration of IFN γ -producing HPV16 and/or HPV18 E2 (complete, N-terminal, and/or C-terminal peptide pools), E6 and/or E7-specific T cells
ChipCytometry	Analysis of T cell responses to the separate or combined protein peptide pools of HPV16 and/or HPV18 E2, E6, and E7 proteins in PBMCs, including but not limited to CD4 ⁺ and CD8 ⁺ T cells producing IFN γ , TNF α and/or IL-2

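### Could pooling HPV16 and HPV18 women in the immunogenicity analysis tilt the Regimen 3 versus Regimen 2 comparison?

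*Protocol*

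**What the plan says.** Section 11.5 groups the immunogenicity summaries as follows: "Immunogenicity analyses for HPV16 and HPV18 participants will be performed either combined or by HPV type (HPV16 or HPV18), and by infection type". Results are descriptive (geometric means with 95% CIs, or medians and quartiles), and no hypothesis is tested.

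The regimens differ in the antigens given at Dose 1. Section 3.2 describes the Ad26 component of Regimens 1 and 2 as "matching the participant's underlying HPV infection". Regimen 3 gives both components to every woman, and Section 3.2 adds that it "will be used to assess safety and immunogenicity and data will be compared to regimen 2". The MVA vaccine at Dose 2 carries both HPV16 and HPV18 antigens in all active regimens (Section 14.1).

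The secondary endpoint in Section 2.1 is "T cell responses to the separate or combined protein peptide pools of HPV16 and HPV18 E2, E6 and E7 proteins". Section 9.2.2 says "cellular immune responses will be measured in all participants at 5 time points". Neither section states that each woman's cells are tested against both types' pools, but that is the reasonable reading.

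For viral clearance only, footnote a of Section 2.1 explains the combined result: "The sum of women who clear an HPV16 infection plus women who clear an HPV18 infection".

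**The concern.** Read literally, Section 11.5 accepts a combined analysis as an alternative to one by HPV type and does not say which antigen's response is combined. If the response to, say, the HPV16 pools were pooled over all women in a regimen, half of Regimen 2 would have had no HPV16 antigen from the Ad26 dose, while all of Regimen 3 would have had it. The two regimens would then differ in antigen exposure as well as in mixing and in the amount per component. Regimen 3 could look stronger even where the response to the infecting type is the same or lower.

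The worry is not far-fetched. The sample-size section already treats a regimen as one group of 20 over both HPV types. Section 5 also lets the mix change, since "up to 8 HPV18-infected participants can be replaced by HPV16-infected participants", so the size of any artefact would move with enrolment. At stake is how the Regimen 3 versus Regimen 2 contrast is read when the next regimen is chosen.

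**Working it through.** **The plan's own figures.** Section 11.2 gives bounds for zero observed reactions, and both reproduce: 1 − 0.05^(1/20) = 13.9% and 1 − 0.05^(1/48) = 6.1%. They concern safety. The protocol gives no figure for immunogenicity.

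**Inputs from Table 4.** Regimen 2 has 10 HPV16 and 10 HPV18 women, and so does Regimen 3. For a given antigen, the share of Regimen 2 not primed with it at Dose 1 is f = 10/20 = 0.5. In Regimen 3 that share is 0.

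**Assumed quantities, not in the protocol.** Let k be the fold by which the matching Ad26 prime in Regimen 2 raises the response over no matching prime. Let m be the true Regimen 3 to Regimen 2 ratio of geometric means on the matched antigen. Assume multiplicative effects and the same infection mix in both regimens.

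**Single antigen pooled over HPV type.** Apparent ratio = m × k^f, here m × k^0.5. It ties at m = k^(−0.5).

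| k | m = 1 | m = 2/3 | m = 1/2 | m at which it ties |
|---|---|---|---|---|
| 1 | 1.00 | 0.67 | 0.50 | 1.00 |
| 2 | 1.41 | 0.94 | 0.71 | 0.71 |
| 3 | 1.73 | 1.15 | 0.87 | 0.58 |
| 5 | 2.24 | 1.49 | 1.12 | 0.45 |

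The columns with m below 1 matter because Regimen 2 gives 1×10^11 vp of the matched component and Regimen 3 gives 5×10^10 vp of each. If the larger amount adds enough response, the pooled ratio still falls below 1. The shift is towards Regimen 3, but the table need not favour it.

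**After the full optional replacement of 8 women.** At the Step 5 ratio of 6:6:4, 8 × 6/16 = 3 women move in each of Regimens 2 and 3, giving 13:7 (an assumption). With m = 1 and k = 2, 3 and 5:
- HPV16 pools, f = 7/20 = 0.35: 1.27, 1.47, 1.76.
- HPV18 pools, f = 13/20 = 0.65: 1.57, 2.04, 2.85.

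**By HPV type, or combined on the matched antigen.** Every Regimen 2 woman counted was primed with the antigen measured, so f = 0 and the ratio is m for every k. There is no artefact.

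**When k could be large.** Of the four post-baseline cellular samples, only the pre-Dose 2 sample reflects Ad26 alone. The other three follow an MVA dose carrying both antigens, so k may be smaller there. Cross-reactivity between HPV16 and HPV18 pools would also pull k towards 1.

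**Precision of the two sound options.** The 95% CI half-width for a difference of two log means is t(0.975, 2n−2) × √(2/n). It is 2.101 × 0.447 = 0.94 SD at n = 10 (by type) and 2.024 × 0.316 = 0.64 SD at n = 20 (matched antigen, combined). The current wording allows both.

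**The case for a change.** The best case for a change is that the protocol does more than stay silent: its either/or wording puts the vulnerable grouping on a par with the sound one. The type-matched meaning of combined is attached only to clearance, and immunogenicity is where the other type's antigen is also measured. The Synopsis paragraph on immunogenicity has no grouping by type, although its virology paragraph does. Sponsor statisticians are unblinded at the primary analysis, so the meaning should be settled before then. A clarifying sentence would cost no samples or assays.

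Part of this stands. The word is undefined in Section 11.5, the arithmetic is right, and a single-antigen pooled table read as strength of response to the infecting type would mislead.

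The rest does not make a defect. The misleading table is one the protocol nowhere specifies. Section 11.6 uses nearly the same grouping phrase, and there its meaning follows the infecting type; nothing suggests Section 11.5 intends the opposite. Randomisation is stratified by HPV type, and Tables 1 and 4 label Regimens 2a and 2b separately, so the data are organised along the line the concern fears will be lost. A shorter Synopsis is not a contradiction. A total response to both types' pools is a legitimate question about breadth. Which antigen enters which table is detail that a protocol normally leaves to the SAP, and the opening of Section 11 says that specifics will be given there.

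**Conclusion.** No change to the protocol follows. The concern identifies a real way to misread a table, but it needs three steps the protocol does not take: choosing the combined option, using a single antigen for it, and reading the result as the response to the infecting type. The analysis by HPV type named in the same sentence avoids the problem entirely, and so does the natural matched-antigen reading of combined.

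If the misleading table were made, the ratio would be shifted by k^0.5, that is 1.4 to 2.2 for k from 2 to 5, and by nothing at k = 1. This rests on an assumed k and on multiplicative effects, and it is most plausible at the pre-Dose 2 sample. The pooled ratio could still favour Regimen 2, for example 0.87 at k = 3 and m = 1/2. No error rate, sample size or decision rule depends on the comparison. This is a gap in wording that an analyst who knows the design would fill correctly; the SAP is not among the documents at hand and may already do so.
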